### INTRODUCTION AND GENERAL INFORMATION

Nowadays, both esthetic concerns and ecological awareness have led to the preference of composite resin instead of amalgam in most restorations. However, the acidic adhesive monomers used during the application of composite resins can cause pain following restoration. This type of pain, defined as postoperative sensitivity, generally occurs independently of restoration failure and is reported by patients at different levels and intensities. Typically, this pain lasts for a period of several days to one month after the restoration and then subsides. In rare cases where severe pain occurs, endodontic treatment may become necessary (1).

Postoperative sensitivity may arise due to several factors, including the remaining dentin thickness, the diameter and patency of dentin tubules after acid etching, the general condition of the pulp, and clinician-related factors (2). To reduce postoperative sensitivity, several approaches have been suggested, such as avoiding excessive drying during cavity preparation (3), applying desensitizers and liners to the cavity (2), and using self-etch adhesives (4). However, current evidence shows that the type of adhesive itself is not a determining factor for postoperative sensitivity (5). It has also been reported that desensitizers applied to the cavity may influence bond strength. Therefore, careful selection of the material to be applied is important for the success of the restoration.

Teethmate Desensitizer (Kuraray Noritake), a desensitizing agent containing tetracalcium phosphate and dicalcium phosphate anhydrous, forms hydroxyapatite through a dissolution-precipitation reaction. An in vitro study demonstrated that this material does not adversely affect bond strength (6). Another in vitro study (7) reported that while Teethmate Desensitizer reduced adhesive bond strength, it also decreased microleakage. For this reason, it was suggested that in multimode adhesives used in self-etch mode, Teethmate Desensitizer could be applied to the cavity before adhesive application in order to reduce postoperative sensitivity.

Although the effectiveness of Teethmate Desensitizer in occluding dentin tubules and reducing sensitivity has been reported in clinical studies (8–10), no study investigating its effect on postoperative sensitivity following composite resin restorations has been identified.

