### Statistical Pre-analysis:

The sample size was calculated using the online calculator at [www.sealedenvelope.com](http://www.sealedenvelope.com). Assuming a power of 90% and an error margin of 5%, the required number for each group (experimental and control teeth) was found to be 43. Since a split-mouth design will be used, in which each patient will have both experimental and control groups, the required number of participants was also determined to be at least 43. Considering possible dropouts during the study, the final sample size was set at 50 participants. Randomization will be achieved using a blocked randomization technique at [www.sealedenvelope.com](http://www.sealedenvelope.com). For blocked randomization, the seed number will be set as 12345 and block size as 2.

In the second phase, volunteer participants will be selected among patients who apply to the Faculty of Dentistry, Başkent University, and are referred to the Department of Restorative Dentistry for treatment after clinical and radiological examination revealed carious lesions. The inclusion criteria will be as follows:

- Voluntary acceptance of participation in the study
- Age between 18–65 years
- Presence of at least 12 teeth in occlusion
- The teeth to be included must have natural antagonists and adjacent teeth (normal occlusion)
- Anterior or posterior teeth with primary or secondary carious lesions in which the cavity preparation is expected to approach the pulp closely but without pulpal exposure
- Each participant must have two teeth, one on the right and one on the left, fulfilling the above criteria
- Absence of any other factor causing sensitivity or pain that might interfere with evaluation

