### Exclusion criteria:

- Refusal to participate in the study
- Age under 18 or over 65 years
- Presence of dental or orofacial pain
- Presence of bruxism
- Presence of advanced periodontal disease
- Presence of systemic diseases that may hinder treatment procedures or follow-up visits
- Teeth with excessive loss of tooth structure requiring full crown restoration, or with severe attrition, cracks, or non-vital teeth
- Pulpal exposure during cavity preparation
- Presence of gingival recession
- Use of analgesics, anti-inflammatory, or psychotropic drugs within the last 15 days or currently using them
- Pregnancy or lactation
- Known allergy to the materials to be used

Eligible individuals will be invited to participate in the study after verbal explanation

of the purpose and methodology. Participation will be voluntary, and those who accept will sign an Informed Consent Form. If deemed necessary, participants will receive oral hygiene motivation, and interventions will begin once oral hygiene has reached a satisfactory level.

In the third phase, before starting treatment of the teeth diagnosed with caries through clinical and radiological examination, vitality tests will be performed. After cavity preparation of two teeth per participant, the cavities will be isolated. At the point closest to the pulp, a calcium hydroxide-based pulp capping agent (Dycal, Dentsply Sirona, York, USA) will be applied in paste form. Subsequently, Teethmate Desensitizer will be applied according to the manufacturer's instructions to one cavity randomly, while the other will receive no desensitizer. To ensure randomization, pre-prepared allocation lists from [www.sealedenvelope.com](http://www.sealedenvelope.com) will be placed in opaque envelopes, which will be opened only at the time of intervention.

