When necessary depending on cavity type, a matrix system (Mylar strip, sectional matrix, or Tofflemire) will be applied before restoration. All cavities will be treated with a one-step self-etch adhesive (Clearfil SE Bond, Kuraray Noritake, Tokyo, Japan) according to manufacturer's instructions and light-cured with an LED unit (LedMax Cordless 550, Benlioğlu Dental, Ankara, Turkey) at a constant intensity  $>1,500$  mW/cm^2 for 10 seconds. Restorations will be completed using a universal composite resin (Filtek Z250, 3M Espe, St. Paul, MN, USA) with the oblique incremental technique. Each increment of composite will be polymerized for 20 seconds with the same LED device. Finishing and polishing will be performed using diamond finishing burs, polishing rubbers, and disks (Soflex, 3M Espe, St. Paul, MN, USA). All restorations will be performed by a single operator.

After restoration, participants will be given two forms (one for each tooth) to record their daily pain levels for one week. Instructions for filling out the forms will be provided. The forms will include the Numerical Rating Scale (NRS, 0–4) and the Visual Analog Scale (VAS, 0–100 mm). One week later, patients will return for follow-up, and the completed forms will be collected. Six weeks after the restorations, patients will return for another follow-up. At both the one-week and six-week follow-up visits, restorations will be evaluated by another dentist to ensure double blinding.

At the one-month control visit, tooth vitality will first be assessed. If the tooth is vital, postoperative sensitivity will be evaluated using VAS scores and by applying a cold spray (Ice Spray, Picdare S.p.A, Casnate con Bernate, Italy) with a cotton pellet to the mid-buccal surface of the teeth for 5 seconds.

Study Start Date: May 3, 2021

Study Completion Date: May 3, 2022

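### The late visit scores sensitivity only in teeth that are still vital and the analysis counts the others nowhere, so the late comparison is open to selection bias of unknown direction

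*Combined protocol and SAP*

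**What the plan says.** The follow-up text in Materials and Methods (after the exclusion list) sets the order of the late assessment: "At the one-month control visit, tooth vitality will first be assessed". It continues: "If the tooth is vital, postoperative sensitivity will be evaluated using VAS scores", together with a cold spray on the buccal surface. One condition governs both measures.

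Three other statements bear on this:

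- **Entry.** The exclusion criteria rule out teeth with "severe attrition, cracks, or non-vital teeth", and before treatment "vitality tests will be performed".
- **Population.** The inclusion criteria select teeth for which "the cavity preparation is expected to approach the pulp closely but without pulpal exposure".
- **Background.** The Introduction says of pain after composite restorations: "In rare cases where severe pain occurs, endodontic treatment may become necessary".

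The earlier outcome has no such condition: "participants will be given two forms (one for each tooth) to record their daily pain levels for one week".

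The Statistical Analysis section names a chi-square test for NRS and an independent two-sample t-test for VAS. It defines no analysis set and has no rule for an unscored tooth, and loss of vitality is not listed as an outcome. No time point is named as primary. The same follow-up text describes a six-week follow-up and then a one-month control visit, and does not say whether they are the same visit.

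**The concern.** Every enrolled tooth is vital at the start, so a tooth that is non-vital at the late visit became so after it was randomised and treated. Whether a tooth is scored then depends on an event that the agent under study might make more or less frequent. What remains is a comparison of teeth whose pulp survived, and randomisation no longer guarantees that these are alike in the two arms.

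The consequence could go either way. If the desensitizer prevents severe reactions, the worst control teeth go unscored and a benefit is understated. If it harms the pulp, the affected treated teeth go unscored, the treated arm looks better than it is, and the harm appears in no planned table.

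The Introduction links severe pain to endodontic treatment, so the unscored teeth may include the extreme of the outcome being studied. Because no time point is primary, the late comparison cannot be set aside as secondary.

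**Working it through.** **The plan's own figure.** There is none to reproduce: the documents give no rate of vitality loss or endodontic treatment in either arm. All rates below are assumptions.

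**Step 1. Will a rule be needed?** 50 participants with two teeth each give 100 teeth. With rate p per tooth and independent teeth, the chance of at least one loss is 1 − (1 − p)^100.

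- p = 1%: 1 − 0.99^100 = 63%.
- p = 2%: 1 − 0.98^100 = 87%.

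Even a rare event would probably occur at least once.

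**Step 2. How far could the late difference move?** Take late scores as normal with SD 1, a true difference (control minus treated) of 0.40 SD and within-pair correlation 0.5. Take the unfavourable case, in which the teeth lost are the highest scorers. Losing the top fraction p of an arm lowers the mean of the remaining teeth by

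m(p) = φ(z) / (1 − p),

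where z is the (1 − p) normal quantile and φ the normal density.

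- p = 6%: z = 1.555, φ = 0.1191, m = 0.1191/0.94 = 0.127.
- p = 1%: z = 2.326, φ = 0.0267, m = 0.0267/0.99 = 0.027.

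*Unpaired comparison, as planned.* The unscored tooth leaves and its partner stays:

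observed difference = 0.40 − m(control) + m(treated) = 0.40 − 0.127 + 0.027 = 0.30 SD, a distortion of 0.10 SD.

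*Paired comparison, both teeth scored.* The partner leaves too. With correlation 0.5 it carries about half of the shift, so about half of the distortion cancels:

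observed difference ≈ 0.40 − 0.5 × (0.127 − 0.027) = 0.35 SD, a distortion of 0.05 SD.

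Simulation of the same set-up gives 0.30 and 0.35 SD.

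**Step 3. Other assumed rates**, with m(2%) = 0.049:

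| Loss, control / treated | Teeth lost | Unpaired | Paired |
|---|---|---|---|
| 2% / 2% | highest scorers | 0.40 | 0.40 |
| 2% / 1% | highest scorers | 0.38 | 0.39 |
| 6% / 1% | highest scorers | 0.30 | 0.35 |
| 1% / 6% | highest scorers | 0.50 | 0.45 |
| 6% / 1% | unrelated to VAS | 0.40 | 0.40 |

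The true value is 0.40 in every row. The distortion in the unpaired column is m(control) − m(treated), so it does not depend on the choice of 0.40. It disappears when loss is equal in number and type, or unrelated to VAS, and it changes sign when the arms are exchanged.

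**The case against.** A reader might infer that the treatment comparison is biased. The documents do not show that. Bias requires the number or type of teeth lost to differ between arms. No rates are given, the only word on frequency is that severe cases are rare, and the direction could be either. That word describes composite restorations in general. A higher rate in near-pulp cavities is plausible, but no figure supports it. Nor do the documents say that a tooth which has lost vitality would score high on the late VAS; if it would not, the table shows no distortion.

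A reader might also infer that the whole trial is affected, or that each unscored tooth removes its pair. Neither follows. The one-week diary covers both teeth without a vitality condition. Under the planned independent t-test the partner tooth stays in, although the working shows that this comparison is then more exposed, not less.

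The vitality check can be defended for the cold test. A non-vital tooth is not expected to respond, and scoring it as zero would count a failure as a good result. This stands, and the fix keeps the check there. It does not extend to the VAS, which the patient can give for any restored tooth.

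Finally, giving failed teeth the worst score turns sensitivity into a composite of sensitivity and pulp failure, and can itself add apparent signal. That also stands, and is why it is proposed only as a sensitivity analysis.

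**Conclusion.** The concern holds in a limited form. The rule as written removes teeth from late scoring because of a post-randomisation event that treatment may affect, and the analysis section accounts for them nowhere. This is a flaw in the stated rule and not just missing detail. It leaves the late-visit comparison open to selection bias of unknown direction, and could keep a pulpal harm out of the results.

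The size cannot be determined from the documents. Under the assumptions shown (normal scores, correlation 0.5, highest scorers lost) it runs from none, through about 0.01 SD paired at 2% against 1%, to about 0.05 SD paired and 0.10 SD unpaired at 6% against 1%. A wider gap between the arms would give more. These figures illustrate what is possible and are not an estimate for this trial. The case for change rests on the rule and on how little it costs to correct.

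**What to change.** **Materials and Methods, late visit**

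- Make only the cold test conditional on vitality, and record the late VAS for every restored tooth.
- Reconcile the six-week and one-month descriptions, so that it is clear at which visit this assessment takes place.

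**Statistical Analysis**

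- Report teeth that lost vitality or had endodontic treatment by arm as an outcome, as counts with the number of discordant pairs. Such a failure is then neither dropped nor read as a low score.
- Pre-state a sensitivity analysis of the late visit that keeps every randomised pair and counts such teeth as the worst outcome, and show the vital-only result beside it.

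**Cost.** A few sentences and one table, with no new visit or test. The worst-outcome score is a convention and, where loss is equal in the two arms, may cost some power, so it should not replace the main analysis. With few events the counts will be imprecise, and a formal test on them would have little power.

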## STATISTICAL ANALYSIS

Measurements will be obtained from two paired teeth of the same patient. The VAS and NRS values of these paired groups will be compared. For this purpose, chi-square test will be used for NRS values, and independent two-sample t-test will be used for VAS values. The significance level will be set at  $p = 0.05$ .

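### Paired right and left teeth are to be compared with independent-sample tests; ignoring the pairing is the main loss, and omitting treated side is a smaller, conditional one

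*Combined protocol and SAP*

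**What the plan says.** The design is split-mouth. Under Statistical Pre-analysis, the inclusion criteria state: "Each participant must have two teeth, one on the right and one on the left, fulfilling the above criteria". The text after the exclusion criteria has the agent placed in one of the two cavities at random, from a prepared list in opaque envelopes. On how the list is made, the plan says: "For blocked randomization, the seed number will be set as 12345 and block size as 2". It does not say what a block consists of, or whether the list is coded by side.

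The Statistical Analysis section notes that the measurements come from two teeth of one patient, and continues: "The VAS and NRS values of these paired groups will be compared". The tests it names are a chi-square test for NRS and an independent two-sample t-test for VAS, at a level of 0.05. Neither uses the patient as a matching factor, and neither includes side.

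**The concern.** A split-mouth trial gains its efficiency from comparing two teeth in the same mouth. If teeth in one mouth tend to give similar scores, a test for independent samples uses a standard error that is too large. The interval is then too wide, the true level falls below the stated one, and power is lost.

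Side raises the same kind of question on a smaller scale. It differs within every pair, and the allocation fixes which side is treated, so it plays the part that period plays in a cross-over trial. If treated side is balanced across participants, a constant right-left difference cancels from the treatment estimate but stays in the error variance unless the analysis has a side term. If treated side is not balanced, the difference adds real noise to the estimate, which the same term removes.

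What is at stake is precision and power. Randomisation protects the treatment estimate from bias in either case.

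**Working it through.** **Inputs from the documents.** Level 0.05, taken as two-sided because sidedness is not stated; 90% power; 43 pairs required and 50 planned; one right and one left tooth per pair; block size 2.

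**Assumptions, not in the documents.** Within-patient correlation ρ from 0 to 0.7. Right-left difference d from 0 to 0.5 SD of the within-patient difference. Normal scores. At ρ = 0.5 the SD of the within-patient difference is √(2 × (1 − 0.5)) = 1 tooth-level SD, so the two scales agree there.

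**The plan's own figure.** The plan gives 43 teeth per group, and the sentence that leads to it reads: "Assuming a power of 90% and an error margin of 5%, the required number for each group (experimental and control teeth) was found to be". No effect size or SD is given, so 43 can only be back-solved. For two independent groups, n = 2(1.960 + 1.282)²/δ². With δ = 0.70 this is 2 × 10.51/0.49 = 42.9, which rounds up to 43. The figure is therefore consistent with a calculation that makes no use of pairing, but this cannot be confirmed.

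**Step 1: ignoring the pairing, no side effect.** The true variance of the difference in means is 2(1 − ρ)/n in tooth-level SD units, while the independent t-test uses 2/n. Its interval is too wide by the factor 1/√(1 − ρ). Levels below are simulated with 50 pairs.

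| ρ | Interval too wide by | True level of planned t-test |
|---|---|---|
| 0 | 0% | 5.0% |
| 0.3 | 20% | 2.1% |
| 0.5 | 41% | 0.6% to 0.8% across runs |
| 0.7 | 83% | 0.06% |

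For ρ = 0.5, a large-sample check gives 1.984/√0.5 = 2.806, a two-sided tail of 0.5%. Simulated power for an effect of 0.45 SD at ρ = 0.5 is 64% for the planned test and 88% for a paired t-test.

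**Step 2: omitting side once the pairing is respected.** Write D = τ + d·S + e for treated minus control, with S = +1 if the right tooth is treated, −1 if the left, and e of variance 1. A paired test without side estimates the variance of D as 1 + d², so its standard error carries a factor √(1 + d²): 1.02 at d = 0.2 and 1.12 at d = 0.5.

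- If blocks of 2 run over participants, S averages to zero over 50 pairs. The true variance of the estimate is 1/n, and the extra d² is charged for nothing.
- If a block is one patient's two teeth, S is in effect randomised separately in each participant. The d² is then real variance, so the level is correct but precision is lost.

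Simulated results use 50 pairs and τ = 0.468, which gives 90% power for a paired t-test when d = 0:

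| Block of 2 | d | Level, no side term | Power, no side term | Power, side term |
|---|---|---|---|---|
| Two participants | 0 | 5% | 90% | 90% |
| Two participants | 0.2 | 4.6% | 89% | 90% |
| Two participants | 0.5 | 2.8% | 85% | 90% |
| One patient's teeth | 0.2 | 5% | 89% | 89% |
| One patient's teeth | 0.5 | 5% | 83% | 89% |

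If a block is one patient's teeth and d = 0, the side term loses about 0.6 power points.

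**Step 3: the two omissions compared in the planned test.** In the independent t-test, omitted side widens the interval by √(1 + d²/4), with d in tooth-level SDs: 0.5% at 0.2 and 3.1% at 0.5. Ignoring the pairing at ρ = 0.5 widens it by 41%. At ρ = 0.5, with side blocked over participants, the planned test's level is about 0.5% at d = 0.2 and 0.4% at d = 0.5. It was already below 1% with no side effect.

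**The case against.** The strongest case against the side term is that no right-left difference is documented. A reader might infer one, because the Introduction lists "the general condition of the pulp, and clinician-related factors" among the causes of sensitivity and the restoration procedure says "All restorations will be performed by a single operator". Neither passage mentions side, access or handedness. Together they make a side effect possible but do not show one. The criteria also admit anterior and posterior teeth without matching the pair on arch or tooth type, so part of any access effect could vary between pairs and escape a constant side term. The assumed 0.5 SD exceeds the treatment effect of 0.468 used in the power figures, and at 0.2 SD the gain is about one power point. All of this stands, and it limits side to a secondary refinement.

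A reader might also infer that side is the blocked quantity, so that any test without side is conservative. The documents do not say what a block contains. If it is one patient's two teeth, a paired test without side keeps its level, so the claim of conservatism holds under only one of two open readings.

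Finally, a reader might credit side with the wide intervals and low level of the planned test. Step 3 shows that these come almost wholly from the ignored pairing.

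The objection does not remove the point. The mismatch between paired data and independent-sample tests is in the text itself. A plain paired test would still omit side, and including side costs almost nothing.

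**Conclusion.** The point holds in two unequal parts. The main fault is that data described as paired are to be analysed as independent. Its size depends on the within-patient correlation, which the documents do not give. At 0.5 the planned t-test runs at about 0.6% instead of 5%, with an interval 41% too wide; at zero correlation nothing is lost. No corresponding figure was computed for the chi-square test on NRS, which ignores the pairing in the same way.

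Omitting treated side is secondary and depends on a right-left difference that is assumed. Over 0 to 0.5 SD of the within-patient difference, the cost to a paired test runs from nothing to about 5 power points if blocks run over participants, and to about 7 points (90% to 83%) if they do not. The level falls below 5% only in the first case.

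For positive within-patient correlation, the errors found are in the conservative direction. They do not show a biased treatment estimate or an inflated false-positive rate.

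**What to change.** In the Statistical Analysis section, replace both independent-sample tests with a within-patient analysis.

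- **VAS:** regress the treated-minus-control difference on treated side, coded +0.5 for right and −0.5 for left, and report the intercept as the treatment effect with its 95% interval. Keep this fixed coding. Centring the code at its sample mean would return the unadjusted mean difference whenever the sides are unequal.
- **NRS:** use a paired ordinal method such as the Wilcoxon signed-rank test, or compare right-minus-left differences between participants allocated right and those allocated left with a rank-sum test.
- **Record analysed:** name which of the daily or follow-up scores each test uses, since neither test can be applied without that.

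Under Statistical Pre-analysis, state what a block of 2 contains and whether the list is coded by side.

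The cost is a few sentences and one degree of freedom. No new data are needed, because side follows from the allocation and from the form kept for each tooth. The only statistical downside is about 0.6 power points if side has no effect and the blocks do not balance it.

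### Paired teeth are to be compared with tests for independent groups, so the analysis does not match the split-mouth design

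*Combined protocol and SAP*

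**What the plan says.** The Statistical Pre-analysis section sets the design: "Since a split-mouth design will be used, in which each patient will have both experimental and control groups". The treatment description that follows the exclusion criteria confirms assignment within the patient, with desensitizer applied "to one cavity randomly, while the other will receive no desensitizer". Patients complete one form per tooth, each carrying a five-grade NRS (0–4) and a 0–100 mm VAS.

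The Statistical Analysis section opens with "Measurements will be obtained from two paired teeth of the same patient" and continues "The VAS and NRS values of these paired groups will be compared". Its next sentence names the methods: "chi-square test will be used for NRS values, and independent two-sample t-test will be used for VAS values". The significance level is 0.05. No paired method is named anywhere in the document, and no confidence interval is planned. The chi-square test is not described further, so its ordinary form (unpaired, categories unordered) is the natural reading.

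**The concern.** The section describes paired data and then names two tests that require independent groups. The same person scores both teeth, so the two scores share that person's pain threshold and way of using the scale. An independent t-test is valid here only if the within-patient correlation is zero, and a split-mouth design gains precision only when that correlation is positive. The named test therefore uses none of the gain.

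The NRS comparison has a second, separate fault. A chi-square test across five grades treats them as unordered, which spreads its sensitivity over 4 degrees of freedom, and it meets sparse cells if most teeth score 0 or 1.

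These are the only planned comparisons of the trial's outcomes. If they come out non-significant, the reader cannot tell an ineffective desensitizer from an insensitive test.

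**Working it through.** **Inputs from the document.** 43 patients, each with one treated and one control tooth (Statistical Pre-analysis: "the required number of participants was also determined to be at least 43"); 5% level; 90% power; NRS with five grades; VAS 0–100 mm. Two-sided testing is assumed, because sidedness is not stated.

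**Inputs not in the document.** The within-patient correlation ρ, the effect size, the SD and the NRS grade distribution. All are assumptions below, shown as ranges where possible.

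**The plan's own figure.** 43 per group cannot be reproduced without an effect size. Solved backwards as a two-sample calculation, d = √(2/43) × (1.960 + 1.282) = 0.2157 × 3.242 ≈ 0.70 SD. This is inferred, not stated.

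**Standard errors (VAS).**
- Independent t-test: SD × √(2/n) = 0.2157 SD for n = 43, whatever ρ is.
- Correct for paired teeth: SD × √(2(1−ρ)/n). At ρ = 0.5 this is 0.2157 × √0.5 = 0.1525 SD.
- Ratio of interval widths: 1/√(1−ρ).

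**True type I error of the independent t-test.** 2 × P(t₈₄ > 1.989/√(1−ρ)). The shifted cut-offs are 1.989/√0.7 = 2.377, 1.989/√0.5 = 2.813 and 1.989/√0.3 = 3.631.

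**Power.** From 40,000 simulated trials of 43 bivariate-normal pairs per setting, independent against paired t-test.

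| ρ | True type I error (nominal 5%) | Interval too wide by | Power at 0.4 SD: independent / paired | Power at 0.70 SD: independent / paired |
|---|---|---|---|---|
| 0 | 5.0% | 1.00 | 45% / 44% | 89% / 89% |
| 0.3 | 2.0% | 1.20 | 44% / 58% | 93% / 97% |
| 0.5 | 0.6% | 1.41 | 43% / 73% | 96% / 99% |
| 0.7 | 0.05% | 1.83 | 42% / 91% | 99% / 100% |

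Simulated null rejection rates agree (1.9%, 0.6% and 0.06% at ρ = 0.3, 0.5 and 0.7), and the paired test stays at 5%. At ρ = 0.2 the interval is 1.12 times too wide and the type I error is about 3%. At ρ = −0.2 the error reverses, with a type I error of about 7%.

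The independent test cannot benefit at 0.4 SD because it needs an observed difference of 1.989 × 0.2157 = 0.43 SD to reach significance, however strongly the teeth are correlated.

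**NRS.** Simulated with an underlying normal score cut into five grades, control shares 45/25/15/10/5% (assumed), a shift of 0.70 SD and 2,000 trials per setting:

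| ρ | Chi-square power | Signed-rank power |
|---|---|---|
| 0 | 52% | 75% |
| 0.3 | 54% | 86% |
| 0.5 | 52% | 93% |
| 0.7 | 53% | 99% |

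The 23-point gap at ρ = 0 comes from ignoring the order of the grades. The widening to 46 points at ρ = 0.7 comes from ignoring the pairing. Under the null, chi-square rejects about 2% of the time once ρ is 0.5 or more.

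With more skewed grades (55/25/12/6/2%, assumed), chi-square power is about 45–48% against roughly 80–96% for signed-rank over ρ = 0.3 to 0.7, and about half the expected counts fall below 5. With evenly spread grades the figures are 66–68% against 92–99%, and sparse cells become uncommon.

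**The case against.** The best defence concerns consequences, not the choice of tests.

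- **Effect size.** The only anchor in the document back-solves to about 0.70 SD. At that effect the independent t-test keeps about 93% power or more for ρ of 0.3 and above, and pairing adds only 1 to 4 points. This stands: the VAS power loss falls on smaller effects. But no target effect is stated, so 0.70 SD cannot be relied on, and the NRS comparison is weak even there.
- **Direction.** With positive ρ the error is conservative, so a significant result would remain credible. This also stands. The harm is a missed benefit, unless ρ is negative.
- **Size.** The loss depends on an unknown ρ and is modest at 0.2. True, which is why a range is given. Under any positive ρ, all of the gain from pairing goes unused.
- **NRS attribution.** Part of the NRS loss comes from ignoring grade order, not from ignoring pairing. Correct, and the two are separated above. Both are faults of the same planned test.
- **Wording.** No intervals are planned, so the width ratios apply only to intervals derived from the independent test. The chi-square is not explicitly called unpaired, although nothing in the text suggests otherwise.

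None of this reconciles the named tests with the design.

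**Conclusion.** The concern holds, and the analysis is wrong as written. The contradiction lies within one short section and needs no inference; the rest of the document confirms the paired design and offers no correction. For any non-zero within-patient correlation the t-test does not hold its 5% level, and the NRS test also discards the ordering of its grades.

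The size of the damage rests on assumed values of ρ, the effect and the grade shares. For VAS it runs from slight (ρ near 0.2, or a true effect near 0.70 SD) to severe (power of 42% instead of 91% at ρ = 0.7 and 0.4 SD). For NRS it is substantial under every grade distribution tried. Because both outcome comparisons are affected and the correction is simple, this must be fixed before results are reported.

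**What to change.** In the Statistical Analysis section:

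1. **VAS:** replace the independent t-test with a paired t-test on the within-patient difference (treated minus control tooth), or with the Wilcoxon signed-rank test if clearly non-normal differences are expected. Name one as the main test in advance, so that the choice does not depend on the results.
2. **NRS:** replace the chi-square test with the Wilcoxon signed-rank test on the within-patient difference in grade.
3. **Reporting:** give the mean or median within-patient difference with a 95% CI.
4. **Which score:** state the day or summary from which each difference is formed. The forms collect daily scores for a week and VAS is taken again at a later visit, so the difference is otherwise undefined.

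It would be consistent to restate the sample size using the SD of the within-patient differences, or an assumed ρ.

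The cost is a few lines of wording. No extra patients, visits or measurements are needed, and the paired tests can be applied to data already collected, provided each score stays linked to its patient and tooth.
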